8.3.1 SINGLE ASCENDING DOSE SUBJECT BLOOD VOLUME REQUIREMENTS

Visit Number	Blood volume (mL) required					
	1	2	3	4	5	
Screening	Day 1	Day 2	Day 3	Day 8	TOTAL	
CBC (Lavender top whole blood)	3			3	3	9
Serum Chemistry (SST)	3.5			3.5	3.5	10.5
PT/INR PTT (SST)	2.7			2.7	2.7	8.1
Viral Testing (SST and EDTA)	6.5					6.5
BIO 300 Oral Powder PK (Red top serum)		24 (3cc x 8 draws)	3	3		30
BIO 300 Oral Powder PD (RNA) (PAXgene tube)		20 (5mL x 4 draws)	5			25
Waste associated with use of heparin lock		8				8
Subtotals	9.2	52	8	12.2	9.2	
	STUDY TOTAL					97.1

8.3.2 MULTIPLE SINGLE DOSE SUBJECT BLOOD VOLUME REQUIREMENTS

Visit Number	Blood volume (mL) required										
	1	2	3	4	5	6	7	8	9	10	
Screening	Day 1	Day 2	Day 3	Day 4	Day 5	Day 6	Day 7	Day 8	Day 13	TOTAL	
CBC (Lavender top whole blood)	3			3			3			3	12
Serum Chemistry (SST)	3.5			3.5			3.5			3.5	14
PT/INR PTT (SST)	2.7			2.7			2.7			2.7	10.8
Viral Testing (SST and EDTA)	6.5										6.5

BIO 300 Oral Powder PK (Red top serum)		15 (3cc x 5 draws)				24 (3cc x 8 draws)	3	3		45
BIO 300 Oral Powder PD (RNA) (PAXgene tube)		20 (5mL x 4 draws)				20 (5mL x 4 draws)	5			45
Waste associated with use of heparin lock		5				8				13
Subtotals	11	40		11		63	8	3	11	
			STUDY TOTAL							146.3

8.4 ADVERSE EVENTS AND SERIOUS ADVERSE EVENTS

8.4.1 DEFINITION OF ADVERSE EVENTS (AE)

An adverse event (AE) is defined as any untoward medical occurrence associated with the use of a drug in humans, whether or not considered drug related. Therefore, an AE can be any unfavorable and unintended sign (including an abnormal laboratory finding), symptom, or disease temporally associated with the use of a medicinal (investigational) product, whether or not considered related to the medicinal (investigational) product (attribution of unrelated, unlikely, possible, probable, or definite) (ICH, E2A, E6).

8.4.2 DEFINITION OF SERIOUS ADVERSE EVENTS (SAE)

SAEs that fit any one of the criteria in the SAE definition below must be reported to the Sponsor within 24 hours of awareness of the event.

An adverse event (AE) or suspected adverse reaction is considered "serious" if, in the view of either the Principal Investigator or Sponsor, it results in any of the following outcomes:

- Death;
- A life-threatening adverse event;
- Inpatient hospitalization or prolongation of existing hospitalization;
- A persistent or significant incapacity or substantial disruption of the ability to conduct normal life functions;
- A congenital anomaly/birth defect.

Important medical events that may not result in death, be life-threatening, or require hospitalization may be considered serious when, based upon appropriate medical judgment, they may jeopardize the participant and may require medical or surgical intervention to prevent one of the outcomes listed in this definition.

8.4.3 CLASSIFICATION OF AN ADVERSE EVENT

8.4.3.1 SEVERITY OF EVENT

For adverse events (AEs), guidelines based on the FDA Guidance for Industry Toxicity Grading Scale for Healthy Adult and Adolescent Volunteers Enrolled in Preventive Vaccine Clinical Trials will be used to describe severity. The guidance provides a toxicity grading scale (grade 1, mild; grade 2, moderate; grade 3, severe; grade 4, potentially life threatening) for clinical and laboratory abnormalities. For AE

terminology, the NCI Common Terminology Criteria for Adverse Events (CTCAE) version 5.0 will be used, and AE system organ classification will follow the Medical Dictionary for Regulatory Activities (MedDRA).

8.4.3.2 RELATIONSHIP TO STUDY INTERVENTION

All adverse events (AEs) must have their relationship to study intervention assessed by the clinician who examines and evaluates the participant based on temporal relationship and his/her clinical judgment.

The degree of certainty about causality will be graded using the categories below.

- **Definite** – There is clear evidence to suggest a causal relationship, and other possible contributing factors can be ruled out. The clinical event, including an abnormal laboratory test result, occurs in a plausible time relationship to study intervention administration and cannot be explained by concurrent disease or other drugs or chemicals. The event must be pharmacologically or phenomenologically definitive.
- **Probable** – There is evidence to suggest a causal relationship, and the influence of other factors is unlikely. The clinical event, including an abnormal laboratory test result, occurs within a reasonable time after administration of the study intervention, is unlikely to be attributed to concurrent disease or other drugs or chemicals, and follows a clinically reasonable response on withdrawal.
- **Possible** – There is some evidence to suggest a causal relationship (e.g., the event occurred within a reasonable time after administration of the study intervention). However, other factors may have contributed to the event (e.g., the participant's clinical condition, other concomitant events). Although an AE may rate only as "possibly related" soon after discovery, it can be flagged as requiring more information and later be upgraded to "probably related" or "definitely related", as appropriate.
- **Unlikely** – A clinical event, including an abnormal laboratory test result, whose temporal relationship to study intervention administration makes a causal relationship improbable (e.g., the event did not occur within a reasonable time after administration of the study intervention) and in which other drugs or chemicals or underlying disease provides plausible explanations (e.g., the participant's clinical condition, other concomitant treatments).
- **Unrelated** – The AE is completely independent of study intervention administration, and/or evidence exists that the event is definitely related to another etiology.

8.4.3.3 EXPECTEDNESS

The Principal Investigator will be responsible for determining whether an adverse event (AE) is expected or unexpected. An AE will be considered unexpected if the nature, severity, or frequency of the event is not consistent with the risk information previously described for the study intervention. The final determination of expectedness will be determined by the Medical Monitor in consultation with the Principal Investigator.

8.4.4 TIME PERIOD AND FREQUENCY FOR EVENT ASSESSMENT AND FOLLOW-UP

The occurrence of an adverse event (AE) or serious adverse event (SAE) may come to the attention of study personnel during study visits and interviews of a study participant presenting for medical care, or upon review by a study monitor.

All AEs including local and systemic reactions not meeting the criteria for SAEs will be captured on the appropriate case report form (CRF). Information to be collected includes event description, time of onset, clinician's assessment of severity, relationship to study product (assessed only by those with the

training and authority to make a diagnosis), and time of resolution/stabilization of the event. All AEs occurring while on study must be documented appropriately regardless of relationship. All AEs will be followed to adequate resolution.

Any medical condition that is present at the time that the participant is screened, or after they are screened, but before they are administered the first dose of study drug, will be considered as baseline and not reported as an AE. However, if the study participant's condition deteriorates at any time during the study, it will be recorded as an AE.

Changes in the severity of an AE will be documented to allow an assessment of the duration of the event at each level of severity to be performed. AEs characterized as intermittent require documentation of onset and duration of each episode.

Delegated study personnel will record AEs with start dates occurring any time after the first dose of study intervention is administered through the end of the study. SAEs will be recorded with start dates occurring any time after informed consent is obtained through the end of the study. At each study visit, the investigator will inquire about the occurrence of AE/SAEs since the last visit. Events will be followed for outcome information until resolution or stabilization. Documentation of the serious event will be reported on the Serious Adverse Event CRF and submitted to the Sponsor within 24 hours of awareness.

8.4.5 ADVERSE EVENT REPORTING

The notification process to the study Sponsor of all safety data begins with the completion and submission of the appropriate CRFs or in the case of an initial serious event reporting, by phone.

Investigators are required to report promptly to the Sponsor any adverse events that may reasonably be regarded as caused by, or probably caused by, the drug. If the Adverse Event (AE) meets the Serious Adverse Event (SAE) criteria, the investigator is required to report the event to the Sponsor within 24 hours of awareness.

8.4.6 SERIOUS ADVERSE EVENT REPORTING

The Sponsor will notify the FDA, all participating investigators in a written IND safety report of any adverse experience associated with the use of the drug that is both serious and unexpected and any finding from tests in laboratory animals that suggests a significant risk for human subjects. The Sponsor will submit an IND safety report to the FDA and all participating investigators no later than 15 calendar days after the Sponsor determines that the suspected adverse reaction or other information qualifies for reporting. Unexpected fatal or life-threatening suspected adverse reactions will be reported to the FDA no later than 7 calendar days after the Sponsor's initial receipt of the information. If the FDA requests any additional data or information, the Sponsor will submit it to FDA as soon as possible, but no later than 15 calendar days after receiving the request.

8.4.7 EVENTS OF SPECIAL INTEREST

Subjects that experience any cardiovascular-related events, overdose on the study intervention, have any clinically significant laboratory test abnormalities, or become COVID-19 positive should be reported to the study Sponsor.

8.4.8 REPORTING OF PREGNANCY

Should a participant become pregnant during the study, the Principal Investigator will report this event to the study Sponsor and will create a plan to stop the study intervention as soon as possible. The Principal Investigator will communicate with the physician managing the pregnancy and the subject and pregnancy will be followed to term.

8.5 UNANTICIPATED PROBLEMS

8.5.1 DEFINITION OF UNANTICIPATED PROBLEMS (UP)

The Office for Human Research Protections (OHRP) considers unanticipated problems involving risks to participants or others to include, in general, any incident, experience, or outcome that meets all the following criteria:

- Unexpected in terms of nature, severity, or frequency given (a) the research procedures that are described in the protocol-related documents, such as the IRB-approved research protocol and informed consent document; and (b) the characteristics of the participant population being studied;
- Related or possibly related to participation in the research (“possibly related” means there is a reasonable possibility that the incident, experience, or outcome may have been caused by the procedures involved in the research); and
- Suggests that the research places participants or others at a greater risk of harm (including physical, psychological, economic, or social harm) than was previously known or recognized.

8.5.2 UNANTICIPATED PROBLEM REPORTING

The Principal Investigator will report unanticipated problems (UPs) to the reviewing Institutional Review Board (IRB) and to the Sponsor. The UP report will include the following information:

- Protocol identifying information: protocol title and number, PI's name, and the IRB project number;
- A detailed description of the event, incident, experience, or outcome;
- An explanation of the basis for determining that the event, incident, experience, or outcome represents an UP;
- A description of any changes to the protocol or other corrective actions that have been taken or are proposed in response to the UP.

To satisfy the requirement for prompt reporting, UPs will be reported using the following timeline:

- UPs that are serious adverse events (SAEs) will be reported to the IRB and to the study Sponsor in accordance with the sites policies and procedures and within 24 hours of the investigator becoming aware of the event.
- Any other UP will be reported to the IRB and to the study Sponsor within one week of the investigator becoming aware of the problem.

All UPs should be reported to appropriate institutional officials (as required by an institution's written reporting procedures), the supporting agency head (or designee), and the Office for Human Research Protections (OHRP) within 7 business days of the IRB's receipt of the report of the problem from the investigator.

9 STATISTICAL CONSIDERATIONS

9.1 STATISTICAL HYPOTHESES

Data analysis of the primary endpoints will be based on measurements of genistein aglycone (free genistein) serum concentrations (0-48 h). They will also be based on safety assessments which include blood counts, serum chemistries, urinalysis, ECGs, vital signs, and PTT/INR at the timepoints listed in the **SoA, Section 1.3**. “Baseline” will refer to measurements taken during the screening visit. If no “baseline” data exists from a parameter, then changes in the parameter time regression will be compared.

As this is a single dose escalation and multiple single dose trial evaluating the safety and pharmacokinetic profile of BIO 300 Oral Powder, the statistical hypotheses for the safety measurements is that there will be no change in safety measurements during BIO 300 Oral Powder dosing, and 7 days after the last BIO 300 Oral Powder dose.

For the secondary endpoint, the statistical hypothesis is that there will be a significant change in the level of expression of one or more genes that is attributable to BIO 300 Oral Powder dose.

9.2 SAMPLE SIZE DETERMINATION

The single ascending dose study consists of 4 cohorts, each with at least 6 subjects completing all aspects of the study, split evenly to include at least 3 females and 3 males. As such, 12 females and 12 males will participate for a total of 24 subjects. The multiple single dose study will include at least 8 subjects completing all aspects of the study, split evenly to include at least 4 females and 4 males. This is a sufficient number of subjects in each study to characterize the PK and PD of BIO 300 Oral Powder and to identify DLTs.

9.3 POPULATIONS FOR ANALYSES

All participants will be analyzed. The ITT dataset is the primary dataset for analysis. As a guide, analyses may include, but are not limited to, any or all of the following:

- Intention-to-Treat (ITT) Analysis Dataset: all participants
- Safety Analysis Dataset: participants who took at least one dose of BIO 300 Oral Powder

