1 PROTOCOL SUMMARY

1.1 SYNOPSIS

Title:	A Phase 1 Dose Escalation Trial Evaluating the Safety and Pharmacokinetic Profile of BIO 300 Oral Powder in Healthy Volunteers
Study Description:	
Single Ascending Dose:
 
Open-label, single-dose escalation in healthy volunteers. Each cohort will enroll 8 subjects of which 2 will be backups (1M/1F), so that at least 6 subjects (3M/3F) complete the protocol procedures. The pertinent safety data will be reviewed for each cohort before the next dose level cohort is started. Subjects will follow a diet low in soy isoflavones for 7 days before and 7 days after treatment and will fast at least 8 h before dosing. The test article will be administered on day 1 and the initial dose will be one BIO 300 Oral Powder sachet, 500 mg genistein. Subsequent doses will be 2x the previous cohort. The fourth, and final cohort, dose level will be TBD based on the safety and pharmacokinetic (PK) results from the previous 3 cohorts. Subjects will remain in the clinic 12 hours after dosing for observations and blood sample collection for clinical lab assessment, PK, and pharmacodynamics (PD). Subjects will remain fasted for 4 hours after the test article administration. Subjects will be provided a standardized low soy meal after the 4-hour blood draw and after the 8-hour blood draw. Subjects will return to the clinic on day 2, 3 and 8 after dosing for blood sampling and/or observations as detailed in the schedule of events. Subjects may not miss any clinic visits. At the conclusion of the study, data will be analyzed from all cohorts to determine safety and PK. PD samples will be stored until the completion of all phase 1 studies, and then sent for RNA sequencing and data analysis.

Multiple Single Dose:

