Serum Chemistry and Fasting Lipid Panel – Blood serum will be used to evaluate the blood chemistry parameters. Serum chemistries to include total protein, albumin, sodium, potassium, chloride, bicarbonate, glucose, BUN, creatinine, alkaline phosphatase, ALT, AST, uric acid, LDH, total and direct bilirubin, phosphorous, calcium, magnesium, amylase, lipase, total cholesterol, triglycerides, HDL. Subjects will fast at least 8 h prior to blood collection for serum chemistries.

PTT/INR – Prothrombin Time (PTT) is a test that evaluates a subject’s ability to appropriately form blood clots. The International Normalized Ratio (INR) is a calculation based on results of the PTT that is used to monitor individuals who are being treated with the blood-thinning medication.

Pregnancy Test – Tests will occur at screening, day 1 and during the final visit (SAD, day 8, visit 5; Multiple Single Dose, day 13, visit 10). Tests will use urine or serum for determination of β -HCG.

Viral Testing – Test will occur at screening for both studies. Tests will utilize blood for analysis of the Hepatitis B surface antigen, Hepatitis C antibody, and HIV1 and HIV2 antibody.

Urinalysis – To include pH, specific gravity, dipstick determinations of protein, glucose, ketones and bilirubin, blood and reflex microscopic exam (reflex only if any qualitative measurements or appearance return abnormal)

Concomitant Medications – A record of concomitant medications will be collected for all subjects from the screening visit through BIO 300 Oral Powder treatment and the one-week follow-up phase.

Assessment of Adverse Events – All adverse events (AEs) will be collected from the time the subject takes their first dose of BIO 300 Oral Powder until 7 days after their last dose of BIO 300 Oral Powder. AEs will be documented and submitted to the Sponsor. Any serious AEs (SAEs) will be documented and reported to the Sponsor within 24 hours of awareness (see **Section 8.3**).

Blood-Based Biomarkers – Whole blood will be collected for biomarker analysis. Blood will be collected pre-dose, at several time points around the predicted C_{max} of BIO 300 Oral Powder. The collected samples will be subject to RNA extraction and next-generation RNA sequencing on the Illumina HiSeq platform with paired-end sequencing.

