5.1. Intention-to-Treat Analysis Dataset

The Intention-to-Treat (ITT) analysis dataset will include all study participants

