5.2. Safety Analysis Dataset

All study participants who receive at least one dose of BIO 300 Oral Powder. This analysis set will be used to summarize all safety endpoints.

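### The documents name three different populations for the primary safety and PK analyses and do not say which one governs

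*Combined protocol and SAP*

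**What the plan says.** Protocol 9.3 says "The ITT dataset is the primary dataset for analysis". It defines that set as "Intention-to-Treat (ITT) Analysis Dataset: all participants" and lists a second, narrower set: "Safety Analysis Dataset: participants who took at least one dose of BIO 300 Oral Powder". The list is introduced by "As a guide, analyses may include, but are not limited to, any or all of the following", and the dosed set is not assigned to any table.

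Protocol 9.4.1 closes with a different rule: all data analyses are to be done on those who finished the treatment periods.

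The SAP repeats the broad set in 5.1 ("The Intention-to-Treat (ITT) analysis dataset will include all study participants") but does not call it primary and gives it no analysis. For the dosed set, SAP 5.2 says "This analysis set will be used to summarize all safety endpoints". SAP 5.3 bases PK summaries on dosed subjects with adequate samples. SAP 9.1 reports the proportions with AEs, SAEs and DLTs by dosing cohort and refers to SAP 10, which uses the safety set.

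The design includes standbys. For the single ascending dose (SAD) part the synopsis says "Each cohort will enroll 8 subjects of which 2 will be backups (1M/1F), so that at least 6 subjects (3M/3F) complete" the procedures. The six-day cohort enrols 14, of whom 4 are backups. On collection, protocol 8.2 says "All adverse events (AEs) will be collected from the time the subject takes their first dose of BIO 300 Oral Powder", while 8.4.4 records SAEs from consent onwards.

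**The concern.** The primary endpoint is safety and PK, so the choice of who counts determines the headline result. The three rules can give different answers from the same data. The trial is open label and non-randomised (protocol 6.3), so an intention-to-treat set protects no randomised comparison. It can only add people who had no exposure and for whom non-serious AEs are not collected. A completers set errs in another way: it removes dosed people whose early stopping may itself be the safety signal.

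The documents offer no way to resolve the conflict. The SAP calls the protocol its companion document and gives no order of precedence. Protocol 4.4 says the sponsor will analyse the data under protocol Section 9 for the report to the IND, and protocol 10.1.11 says the first publication will be analysed as the protocol stipulates. Both point to the document that contains the two unsuitable rules.

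**Working it through.** **1. The plan's own count.** Protocol 9.2 and SAP 4 give 4 SAD cohorts with at least 6 completing, plus at least 8 in the six-day cohort: 4 × 6 + 8 = 32. This matches the stated minimum of 32. Recruited without backups: 4 × 6 + 10 = 34. Enrolled with backups, as the synopsis counts: 4 × 8 + 14 = 46.

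**2. The three rules side by side.**

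| Source | Population | Undosed backup | Dosed, stopped early |
|---|---|---|---|
| Protocol 9.3 | all participants | in, if a backup is a participant | in |
| Protocol 9.4.1 | finished treatment | out | out |
| SAP 5.2, 10 | at least one dose | out | in |

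**3. Dilution if 9.3 is followed.** An undosed subject adds 1 to the denominator and nothing to the count of non-serious AEs or DLTs. The relative reduction is 1 − dosed/counted. With no backup dosed:

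- SAD cohort: 1 − 6/8 = 25.0%. For example, 1/6 = 16.7% becomes 1/8 = 12.5%, and 2/6 = 33.3% becomes 2/8 = 25.0%.
- Six-day cohort: 1 − 10/14 = 28.6%. For example, 1/10 = 10.0% becomes 1/14 = 7.1%.
- All cohorts pooled: 1 − 34/46 = 26.1%.

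If backups are dosed in addition to the planned 6 or 10, the reduction shrinks. In a SAD cohort it is 12.5% with one dosed and 0% with two. In the six-day cohort it is 21.4%, 14.3%, 7.1% and 0% with one to four dosed. On the SAP's safety set it is 0% throughout.

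**4. Loss of subjects if 9.4.1 is followed.** Protocol 7.1 makes a DLT a ground for stopping treatment. The six-day cohort recruits 10 and needs 8 to complete, so the design allows two to stop. As an illustration, suppose two of the 10 dosed stop early, each with a DLT, and no backup is dosed:

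- SAP safety set: 2/10 = 20.0%
- Protocol 9.3, backups counted: 2/14 = 14.3%
- Protocol 9.4.1: 0/8 = 0%

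In the SAD cohorts treatment is a single dose, so the completers rule has little effect unless the treatment period is read to include follow-up.

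**5. What is not affected.** An undosed backup has no post-dose laboratory, ECG, vital-sign or PK value, and SAP 7.2 imputes nothing. The broad set therefore cannot dilute post-dose means, changes from baseline or PK parameters. The escalation rules in protocol 7.5 are stated on 6 or 8 subjects, so they do not depend on 9.3.

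**The case against.** The strongest reply is that the SAP already settles the safety denominator. The AE, SAE and DLT proportions appear only in SAP 9.1, which leads to SAP 10 and the dosed set. Protocol 9.4.2 plans means and an ANCOVA, and protocol 9.4.4 summarises AEs without naming a denominator. Protocol 9.3 presents its list of sets as a guide. Protocol 9.2 counts 24 SAD subjects as participating, which is 6 per cohort and leaves the backups out. The completers sentence in 9.4.1 follows a description of t-tests and ANOVA and may have been meant only for those.

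Much of this stands. It rules out treating dilution as the expected result. It does not remove the conflict:

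- The sentence making ITT primary comes before the guide wording and is not qualified by it.
- Whether backups are participants is left open. The synopsis counts them as enrolled, 9.2 suggests they are not counted, and 5.4 uses the word participants even for consented screen failures.
- The completers sentence is written to cover all data analyses.
- The opening of SAP 9 includes all observations whatever the amount of exposure, which does not clearly exclude zero exposure.
- The SAP cites protocol version 1.0, while the history runs to 2.0. The logged changes for 2.0 do not touch populations, so the version gap neither creates nor resolves the conflict.

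**Conclusion.** The point holds as a conflict over populations. Protocol 9.3, protocol 9.4.1 and the SAP give three different answers for the primary safety analysis, with no precedence rule, and the report and publication clauses point to the protocol.

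The size depends on which rule is followed. It is 0% dilution under the SAP. It is 25% in a SAD cohort and 29% in the six-day cohort under 9.3, and this needs three assumptions: 9.3 governs, backups count as participants, and none is dosed. Under 9.4.1 the effect cannot be fixed in advance, because it depends on who stops early. It can remove events as well as subjects.

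A reader might infer that the reported safety proportions will be 25–29% too low, because standbys sit in the denominator and have no adverse events recorded. The documents do not support that. The SAP puts those proportions on dosed subjects. SAEs are recorded from consent, so an undosed backup can contribute an SAE, and the fixed dilution factor applies only to non-serious AEs and DLTs.

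**What to change.** 1. In protocol 9.3, replace the sentence naming ITT as primary with: *The Safety Analysis Dataset (all subjects who took at least one dose) is primary for safety, and the PK Population is primary for PK.* Add the PK Population from SAP 5.3 to the list.
2. In protocol 9.4.1, delete the completers-only restriction or limit it to a named sensitivity analysis.
3. Delete the ITT set from protocol 9.3 and SAP 5.1, or limit it to the disposition table in SAP 8.1. If it is kept, state whether undosed backups belong to it.

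The cost is a few sentences across the two documents. The tables as the SAP already plans them do not change.
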